15. CONFIDENTIALITY

Confidentiality of a patient's personal data is protected by the current laws and legislation. The names and surnames of all patients participating in the trial are strictly confidential. Participants are identified by their initials and the individual number assigned.

The surname and other personal information will not be included in the reports and publications related to this trial. Direct access to the medical records will be available to the trial Monitor, the audit, and representatives of the control bodies when verifying the authenticity of the information obtained during the trial.

16. PARTICIPATION IN THE TRIAL AND COMPENSATION

No payments and/or compensation are provided for participation in this trial. The trial drug, medical examinations, laboratory, and instrumental studies are free of charge for all participants. The patient has the right to information about the results of medical examinations.

In accordance with Article 44 of the Federal Law of April 12, 2010, No. 61-FZ "On the Circulation of Medicines", all patients involved in a clinical trial are subject to compulsory life and health insurance. In the case of harm to the patient's health as a

result of the clinical trial, the patient is obliged to provide the Insurer with an individual identification code for receiving the insurance premium.

17. CALCULATION OF SAMPLE SIZE

No multicenter randomized clinical trials of thrombolytic therapy in ischemic stroke have been conducted in the Russian Federation before. Available scientific literature is related to the pilot application of Actilyse® in a limited number of AIS patients (10-16 people) (V. I. Skvortsova et al., 2006, N. A. Shamalov, 2015). Thus, the data of the SITS-MOST international register and the results of randomized multicenter clinical trials of Actilyse® in comparison with placebo in patients with ischemic stroke were used as the basis for the sample size justification.

The calculation of the number required was carried out taking into account the capacity of 80 % and planning of a non-inferiority study in parallel groups [V. I. Sergienko, I.B. Bondareva "Mathematical statistics in clinical trials"; GEOTAR-Media, Moscow, 2006]. The null hypothesis (H_0) was that the thrombolytic therapy with Fortelyzin® is worse than the standard thrombolytic therapy with Actilyse®. This means that frequency of the primary efficacy criterion in the comparison group (P_{Actilyse}) is higher than in the group of the study drug ($P_{\text{Fortelyzin}}$), taking into account the "no worse" boundary (δ):

$$H_0: P_{\text{Fortelyzin}} - P_{\text{Actilyse}} \leq -\delta$$

The alternative hypothesis (HA) is that Fortelyzin® therapy is no less effective than the standard thrombolytic therapy with Actilyse:

$$H_A: P_{\text{Fortelyzin}} - P_{\text{Actilyse}} > -\delta$$

The calculation of the sample size for the "no worse" hypothesis, the primary criterion representing the proportion of respondents, and even 1:1 distribution in therapy groups is carried out according to the following formula [Chow S-Ch., Shao J., Wang H., "Sample Size Calculations in Clinical Research", 2003]:

$$n = \frac{(z_{1-\alpha} + z_{1-\beta})^2}{(\delta - \Delta)^2} [p_1(1 - p_1) + p_2(1 - p_2)]$$

where n – the number of patients in each of the groups compared;

p_1 – the proportion of **respondents** (reaching the primary efficacy criterion) in the group of the study drug;

p_2 – the proportion of **respondents** in the comparison group with Actilyse®;

$\Delta = p_1 - p_2$ – the expected difference between the proportions of respondents in the groups of the study drug and the comparison drug;

δ – “no worse” boundary

α and β – probabilities of type I and II errors, respectively;

$Z_{1-\alpha}$ and $Z_{1-\beta}$ – critical values of the standard normal distribution.

The limit of clinical significance was chosen to be 16.9% and was calculated as follows.

The frequency of reaching the primary efficacy criterion in the thrombolytic therapy of ischemic stroke using Actilyse®, namely, the percentage of good functional recovery 3 months after thrombolysis (MRS – 0-1 score) according to the International Register (SITS-MOST) is 54.8 % (total number of patients is 6 483) (Wahlgren N et al., SITS-MOST investigators. Multivariable analysis of outcome predictors and adjustment of main outcome results to baseline data profile in randomized controlled trials; Safe Implementation of Thrombolysis in Stroke Monitoring Study (SITS-MOST). *Stroke* 2008; 39: 3316-3322).

The frequency of reaching the primary efficacy criterion when using placebo – the percentage of good functional recovery (MRS-0-1 score) in patients with ischemic stroke 3 months after thrombolysis, is on average 37.9%. This value was obtained according to the ECASS II, Atlantis, and ECASS III studies, where the favorable effect when using placebo was 36.6%, 32 %, and 45.2%, respectively (Hacke W et al, for the Second European-Australasian Acute Stroke Study Investigators. Randomized double-blind placebo-controlled trial of thrombolytic therapy with intravenous alteplase in acute ischaemic stroke (ECASS II. *Lancet* 1998;352:1245-1251),

(Clark W.M., et al., for the Atlantis Study Investigators. for the Second European-Australasian Acute Stroke Study Investigators. Recombinant tissue-type plasminogen activator for ischemic stroke 3 to 5 hours after symptom onset. The Atlantis Study: A Randomized Controlled Trial. *JAMA* 1999;282:2019—26),

(Hacke W, et al. "Thrombolysis with Alteplase 3 to 4.5 Hours after Acute

Ischemic Stroke". ECASS III The New England Journal of Medicine. 2008. 359(13):1317-1329).

Thus, the difference between a good clinical recovery in patients with AIS with the use of Actilyse® and placebo is $54,8\% - 37,9\% = 16,9\%$. Thus, the "no worse" boundary was set as 16%.

Assuming equal proportions of reaching the primary efficacy criterion in the study drug group and the comparison drug group of 54.8% ($\Delta = 0$), with the established "no worse" boundary of 16% and demonstration at the bilateral significance level of 5%, the minimum number of patients included in the trial is estimated as 152 people in each therapeutic group to maintain 80% of the comparison power. Taking into account the possible 10% dropout, it is recommended to increase the sample size to 336 patients (168 patients in each group).

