18. STATISTICAL ANALYSIS OF RESEARCH MATERIALS

For Statistical Analysis R 3.5.1 package will be used.

Normally distributed variables will be described as mean (SD), ordinal variables as median (IQR), and categorical variables as number and percentage per category. For calculation of significant differences between proportions, we shall use the χ^2 method and for medians the Mann-Whitney U test (with a two-sided 5% level of significance). Ninety-five percent confidence intervals will be calculated for quantitative data.

The primary outcome and other continuous variables will be analyzed with a linear regression model. Binary variables will be tested using logistic regression models adjusted for the same stratification variables, p-values for the difference between treatment groups will be extracted from these models.

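### Section 18 contains no test of the non-inferiority hypothesis at -16 points; separately, the 16-point margin takes up nearly all of the alteplase effect it is derived from

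*Combined protocol and SAP*

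**What the plan says.** Sections 8 and 17 describe a parallel-group non-inferiority trial. Section 17 sets the null as a Fortelyzin-minus-Actilyse difference in the primary response proportion at or below minus delta. The alternative, a difference above minus delta, is put into words as "therapy is no less effective than the standard thrombolytic therapy with Actilyse". Section 11 defines the primary endpoint as mRS 0-1 on day 90, a yes/no outcome.

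On the margin, Section 17 first states: "The limit of clinical significance was chosen to be 16.9% and was calculated as follows". It takes 54.8% from a register of 6,483 alteplase patients and subtracts 37.9%, the average over three randomized trials "where the favorable effect when using placebo was 36.6%, 32 %, and 45.2%, respectively". Then the "boundary was set as 16"%. With 54.8% in both arms, 80% power and a two-sided 5% level, "the minimum number of patients included in the trial is estimated as 152 people in each therapeutic group", raised to 168 for dropout.

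Section 18 is the whole of the analysis plan. For proportions: "For calculation of significant differences between proportions, we shall use the" chi-square method. The primary outcome is grouped with continuous variables and given a linear regression. Binary variables get logistic regression, and "p-values for the difference between treatment groups will be extracted from these models". On intervals: "Ninety-five percent confidence intervals will be calculated for quantitative data". The section mentions neither non-inferiority nor the margin.

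**The concern.** A test of difference asks whether the data are compatible with zero. The hypothesis in Section 17 asks whether they rule out -16. These are different questions and can have different answers: a result may be non-significant and still compatible with a deficit well beyond 16 points. With no interval, margin comparison or decision rule written down, the step from data to the primary conclusion would be chosen later, in an open-label trial.

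The second matter is what a pass would mean. A margin almost as large as the assumed benefit of alteplase over placebo leaves little room for error in that assumed benefit. The alternative's verbal form says more than a difference above -16 can support.

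**Working it through.** **1. The plan's own sample size.** Inputs from Section 17: p = 0.548 in both arms, delta = 0.16, expected difference 0, 80% power, two-sided 5% (z = 1.96).

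n = (1.96 + 0.842)² / 0.16² × 2 × 0.548 × 0.452 = 151.9, so 152 per group as stated. A one-sided 5% level would give 120. Dropout: 152 × 1.1 = 167.2, so 168. The trial was therefore sized for a two-sided 95% interval on the risk difference compared with -16.

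**2. What Section 18 offers against that hypothesis.**
- Chi-square: null of zero difference.
- Logistic p-value: null of an odds ratio of 1.
- Linear regression: on a 0/1 outcome the coefficient could be read as a risk difference, but no interval for it and no comparison with -16 is specified.
- 95% intervals: for quantitative data only.

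None of these decides the null at -16.

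**3. What happens if non-significance is read as no worse.** Set the true rates at the edge of the null: Actilyse 54.8%, Fortelyzin 38.8%. Exact binomial enumeration (chi-square without continuity correction; Wald interval for the risk difference):

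| Per arm | Chi-square non-significant | 95% lower limit above -16 |
|---|---|---|
| 152 | 20.5% | 2.5% |
| 168 | 14.9% | 2.4% |

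**4. Where the two readings part.** At 54.8% in both arms and 168 per arm, the 95% half-width is 1.96 × √(2 × 0.548 × 0.452 / 168) = 10.6 points. An observed deficit passes up to about 16 - 10.6 = 5.4 points. Chi-square becomes significant at about 1.96 × √(2 × 0.25 / 168) = 10.7 points. Observed deficits between roughly 5 and 10.7 points are non-significant and yet do not reject the null at -16.

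Example: 76/168 against 92/168. The difference is 45.2% - 54.8% = -9.5 points, SE 5.43. The 95% interval is -9.5 ± 10.6, that is -20.2 to +1.1, and chi-square p = 0.08. The result is non-significant but not non-inferior.

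**5. The margin.** Mean of 36.6, 32 and 45.2 = 37.9; 54.8 - 37.9 = 16.9; 16 / 16.9 = 94.7%, a cushion of 0.9 points. The register's standard error alone is 100 × √(0.548 × 0.452 / 6,483) = 0.62 points, so with the placebo mean treated as exact the lower 95% limit of the contrast is 16.9 - 1.96 × 0.62 = 15.7, below 16. The documents give no placebo sample sizes, so the placebo side's contribution is not computed here; it can only widen the uncertainty.

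**The case against.** The best reply is that the plan omits a step and does not adopt a wrong one. Sections 8 and 17 fix the hypothesis, scale, margin and level, and a competent statistician would infer the interval. That is fair as far as it goes. A reader might infer that the sponsor will declare non-inferiority from p > 0.05. No text says so, and the 20.5% and 14.9% figures hold only under that reading. The omission stands all the same: Section 18 is where the rule belongs, and what it lists are tests of a different null.

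On the margin, 16 is below 16.9, and its size is a design choice open to debate. A reader might infer that a drug no better than placebo would readily pass. The documents' figures do not support that: if 54.8% and 37.9% are both exact, such a drug clears -16 only about 1.7% of the time (normal approximation). Against the three placebo rates singly, the contrast is 18.2, 22.8 and 9.6 points, so two of the three exceed 16. The 15.7 limit is only 0.3 points short, and it matters only if the margin is expected to lie below a lower confidence limit, a standard the plan does not adopt. What stands is that the contrast crosses studies, ignores uncertainty and leaves the step from 16.9 to 16 unexplained.

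The phrase about being no less effective sits directly above the correct formula in a translated text. It is loose wording, not evidence of a planned over-claim. It is also true that any trial clearing a margin supports only that margin; the reason to say so here is how close this margin lies to the whole assumed effect.

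**Conclusion.** The mismatch between Section 17 and Section 18 is established from the text and needs correction before analysis: the primary hypothesis has no specified test. The potential cost is a false acceptance rate of about 15% to 20% in place of about 2.5%, conditional on non-significance being read as no worse, a true deficit of exactly 16 points and 54.8% response on Actilyse. The sample size is not at fault; 152 per group reproduces.

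The margin is a subordinate point. At 94.7% of a register-minus-placebo contrast with no uncertainty allowance, clearing -16 does not by itself show that alteplase's effect over placebo is preserved. The documents do not show that 16 is indefensible, since the within-trial alteplase-minus-placebo differences that could settle it are not given.

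**What to change.** **Section 18.** Make the primary analysis a two-sided 95% confidence interval for the risk difference in mRS 0-1 at day 90, Fortelyzin minus Actilyse. Conclude non-inferiority only if the lower limit is above -16 points. Name the interval method, and say whether it is adjusted and for what: Section 18 refers to stratification variables, but none is named there or in the randomization text of Section 8. State the analysis set and the handling of missing day-90 mRS beside the rule, since Section 7.4 keeps non-completers in the analysis. Remove the primary outcome from the continuous variables. Chi-square and logistic p-values become supportive.

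**Section 17.** State that clearing -16 excludes only a deficit of 16 points or more and does not by itself show that alteplase's effect over placebo is preserved, and word the conclusion accordingly. Alternatively, justify 16 from within-trial alteplase-minus-placebo differences and their uncertainty, which the sponsor would have to supply.

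**Cost.** Some text in two sections; no extra patients and no change to the significance level, because the interval is the test the trial was sized for. The drawback is that a positive result supports a narrower claim.

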18. STATISTICAL ANALYSIS OF RESEARCH MATERIALS

For Statistical Analysis R 3.5.1 package will be used.

Normally distributed variables will be described as mean (SD), ordinal variables as median (IQR), and categorical variables as number and percentage per category. For calculation of significant differences between proportions, we shall use the χ^2 method and for medians the Mann-Whitney U test (with a two-sided 5% level of significance). Ninety-five percent confidence intervals will be calculated for quantitative data.

The primary outcome and other continuous variables will be analyzed with a linear regression model. Binary variables will be tested using logistic regression models adjusted for the same stratification variables, p-values for the difference between treatment groups will be extracted from these models.

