7.1. Inclusion criteria

- Men and women aged 18-80 (inclusive) years old.
- Verified diagnosis of ischemic stroke (neuroimaging (CT/MRI) signs of ischemic stroke, from 5 to 25 points on the NIHSS scale).
- Duration of symptoms of ischemic stroke is not more than 4.5 hours before starting thrombolytic therapy.
- The patient's consent to use reliable contraceptive methods throughout the trial and within 3 weeks after:
 - women who have a negative pregnancy test and use the following means of contraception: intrauterine devices, oral contraceptives, a contraceptive patch, long-acting injectable contraceptives, a double-barrier method of contraception. Women who are not at risk of pregnancy for health-related reasons (documented conditions: hysterectomy, tubal ligation, infertility, menopause for more than 1 year) may also be involved in the trial.);
 - men who use barrier contraception. Men who unable to fertilize (documented conditions: vasectomy, infertility) may also be involved in the trial.
- A participant provided signed and dated informed consent of participation in the trial.

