9. TRIAL PROCEDURES

Visit 1 (Start of the trial)

Prior to administration of the trial drug, all patients will undergo the following procedures:

- determination of inclusion/non-inclusion criteria
- signing of Informed consent
- collection of demographic data (date of birth, sex)
- collection of medical history (duration of the underlying disease, previous therapy, allergological anamnesis, etc.)
- physical examination
- evaluation of changes by organs and systems
- assessment of neurological status using the NIHSS and modified Rankin scales (mRS)
- Duplex scanning of the major arteries of the head (if necessary)
- CT/MRI examination of the brain
- assessment of CT changes according to ASPECTS (Alberta Stroke Program Early CT Score)
- angiography of the cerebral vessels (if necessary)
- blood sampling for hematological and biochemical analyses
- coagulogram
- common urine analysis
- ECG
- assessment of the patient's compliance with the inclusion/exclusion criteria
- randomization

Assignment of individual patient identification code (IPIC)

The Investigator must ensure the anonymity of the trial subjects. The full names of all patients participated in the trial are strictly confidential.

After signing the Informed Consent Form, each patient will be assigned an Individual Patient Identification Code (IPIC) in accordance with the current legislation (Table 6).

Table 6. Individual Patient Identification Code

Permission of the Ministry of Health of the Russian Federation No.	Permission's date of issue, DD/MM/YYYY/	Serial number of the medical organization specified in the Permission	Patient's initials	Patient's date of birth, DD/MM/YYYY/	A unique number assigned to the patient by the Investigator, consisting of letters and numbers (the name of the protocol and the screening number under which the patient was included in the trial)
--	---	---	--------------------	--------------------------------------	--

The individual patient identification code (IPIC) is established by the Insurant based on the patient data provided by the Investigator. The individual patient identification code is reported by the Insurant to the Investigator for inclusion in his medical documentation. The IPIC will be reflected in the primary documentation, Case Report Form, and Patient Information Sheet with the informed consent form. The IPIC will be transmitted by the Code Registry by the Insurant to the Insurer.

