11. EFFICACY ASSESSMENT

This trial involves a comparison group. Evidence of Fortelyzin® efficacy will be compared with the results of the application of Actilyse®.

Criteria for the efficacy evaluation of thrombolytic therapy

- The primary efficacy endpoint is a good functional recovery on day 90 (modified Rankin scale (mRS), 0-1 score).
- Secondary combined efficacy endpoint on day 90 – mRS (0-1) + NIHSS (0-1 score) + Barthel Index (BI) - 95 points or higher.
- Additional efficacy criterion – NIHSS score after 24 hours and after 90 days.

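### Section 18 names no analysis for NIHSS at 24 hours and day 90, and neither analysis it could mean uses the Visit 1 NIHSS

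*Combined protocol and SAP*

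**What the plan says.** Section 11, and the Protocol Summary in the same terms, lists three levels of efficacy criteria. The third reads "Additional efficacy criterion – NIHSS score after 24 hours and after 90 days". No hypothesis, margin, effect size or power is attached to it.

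A pre-treatment value exists for every patient. Section 9 lists, under Visit 1 and before drug administration, "assessment of neurological status using the NIHSS and modified Rankin scales (mRS". Table 5 in Section 8 marks NIHSS at Visit 1. Section 7.1 makes the score a condition of entry: "from 5 to 25 points on the NIHSS scale".

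Section 18 does not mention NIHSS. Three of its rules bear on the question:

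- Description: "ordinal variables as median (IQR". Comparison: "for medians the Mann-Whitney U test (with a two-sided 5% level of significance".
- "The primary outcome and other continuous variables will be analyzed with a linear regression model". No covariates are listed.
- "Binary variables will be tested using logistic regression models adjusted for the same stratification variables". This concerns binary outcomes. No stratification variables are defined anywhere, and Section 8 describes envelope randomisation without strata.

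**The concern.** A score measured on the same scale a day earlier is usually the first covariate to consider. Entry runs from 5 to 25 points, so patients differ widely in severity before any drug is given, and part of the spread at 24 hours is likely to be that earlier spread. An analysis that ignores it counts it as noise.

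Two things are at stake. The first is precision: a real difference in early recovery is harder to see. The second is how a particular result is read: if one arm happens to enter with milder strokes, part of that difference appears in the unadjusted NIHSS comparison. No stratification by severity is described, so neither the design nor the analysis limits this.

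There is also a specification problem. Two sentences of Section 18 could each claim this outcome, and in an open-label trial the choice between them should not be left until data are available.

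**Working it through.** **1. The plan's own figure.** Section 17 sizes the trial on mRS 0-1, with 54.8% in both arms, margin 16%, two-sided 5% and 80% power:

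n = (1.960 + 0.842)² / 0.16² × 2 × 0.548 × 0.452 = 152 per arm, and 152 × 1.1 = 167.2, rounded up to 168.

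This reproduces the stated 152 and 168. It says nothing about NIHSS.

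**2. Which analysis covers NIHSS.**

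| Reading of NIHSS | Analysis under Section 18 | Visit 1 NIHSS used? |
|---|---|---|
| Ordinal | Mann-Whitney U | No; the test takes no covariate |
| Continuous | Linear regression | No; no covariates listed |

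The two readings lead to different tests and share one gap.

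**3. Precision.** Let rho be the correlation between Visit 1 NIHSS and the later score. The documents do not give it; 0.3 to 0.7 is assumed. Adjustment multiplies the outcome variance by 1 − rho². Take an effect that an unadjusted comparison detects with 80% power at 168 per arm, which is (1.960 + 0.842) × √(2/168) = 0.306 outcome SD. Then

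power after adjustment = Φ[(1.960 + 0.842)/√(1 − rho²) − 1.960].

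| rho | Variance removed | Power after adjustment | Patients per arm for the same 80% |
|---|---|---|---|
| 0.3 | 9% | 83.6% | 153 |
| 0.5 | 25% | 89.9% | 126 |
| 0.7 | 51% | 97.5% | 86 |

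The last column is 168 × (1 − rho²), rounded up.

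This formula is for means. A simulation checked the rank-based version (168 per arm, 4,000 runs per setting, baseline confined to 5-25, later score floored at 0, shift of 1.5 points, all distributions assumed):

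| Spearman correlation (approx.) | Mann-Whitney power | Rank ANCOVA power |
|---|---|---|
| 0.44 | 38% | 45% |
| 0.60 | 59% | 81% |
| 0.74 | 81% | 99% |

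**4. Error rate.** With no true effect, the same simulation gave type I error of 4.5% to 5.3% for Mann-Whitney and 5.0% to 5.1% for rank ANCOVA.

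**5. Chance imbalance.** The difference in mean baseline NIHSS has a 95% range of ±1.96 × √(2/168) = ±0.214 baseline SD. With an assumed SD of 5 points that is ±1.07 points. An imbalance at this limit moves the unadjusted comparison by rho × 0.214 outcome SD: 0.064, 0.107 and 0.150 at rho 0.3, 0.5 and 0.7.

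Given an imbalance of exactly that size, the false-positive probability is

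1 − Φ[1.96(1 − rho)/√(1 − rho²)] + Φ[−1.96(1 + rho)/√(1 − rho²)] = 7.9%, 12.9% and 20.5%.

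Given an imbalance of one standard error instead, it is 5.0%, 4.8% and 3.9%. The excess in unlucky draws is offset in the others, which is why step 4 averages to about 5%.

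**The case against.** The strongest reply is that nothing here is invalid. A randomised comparison without covariates already carries chance imbalance in its sampling variance, and steps 4 and 5 bear that out. A reader might infer that imbalance passes in full into the result, or that the false-positive rate is inflated. Neither follows: only a share set by the correlation carries over, and the conditional figures describe unlucky draws, not the procedure's error rate.

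A reader might also infer that the plan commits NIHSS to an unadjusted Mann-Whitney test. It does not. That route rests on treating NIHSS as ordinal, and the linear-regression sentence leaves another open. The reference to the same stratification variables may even hint that the linear model was meant to carry covariates. But none are defined, and baseline NIHSS is named nowhere, so the gap remains on both routes.

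The power figures are fairly called hypothetical. The 80% target in Section 17 belongs to mRS 0-1; the correlation, SD and effect for NIHSS are all assumed, and at rho 0.3 the gain is only about 4 points. The day-90 correlation may also differ from the 24-hour one. Finally, the criterion is third in rank with no decision attached. These points limit the importance of the change; they give no reason to leave the analysis unnamed or the baseline score unused.

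**Conclusion.** The point holds as a gap in specification and a loss of precision for the additional criterion. Section 18 names no single analysis for NIHSS, and no analysis it offers uses the Visit 1 score. That follows from the documents alone.

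The size does not. If the correlation lies between 0.3 and 0.7, an effect seen with 80% power unadjusted would be seen with about 84% to 97.5% power after adjustment, a gain of roughly 4 to 18 points. The direction holds for any positive correlation; the amount is illustrative.

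The documents do not support a claim that the NIHSS comparison would be biased over randomisations, or that its type I error is lost. Nor do they support carrying the point over to the primary mRS non-inferiority conclusion, which is unaffected. The change is worth making because it is cheap and removes a choice of method, not because the planned comparison would be wrong.

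**What to change.** Add to Section 18:

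> NIHSS at 24 hours and at day 90 will each be compared between arms by rank analysis of covariance with treatment and Visit 1 NIHSS as covariate, with patients who died before the assessment given the worst rank. This replaces the linear-regression sentence for NIHSS. The unadjusted Mann-Whitney test is supportive.

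The wording names one method, so no choice is left for later. It specifies the Visit 1 score because Tables 7 and 8 produce many further NIHSS readings on the day of treatment. The rule for deaths is needed because mortality to day 90 is itself an endpoint in Section 12, a patient who has died has no NIHSS, and Section 7.4 keeps randomised non-completers in the efficacy analysis.

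The cost is a short addition to one section. Visit 1 NIHSS is already collected, so no new data, visits or patients are needed. In the simulation, rank ANCOVA kept type I error at about 5%.
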